Фонд за науку
Републике Србије

Utility of plasma drug level monitoring and *CYP2C19* genotyping in dose personalization of escitalopram therapy

PsyCise_E

Principal Investigator: **Asst. [name] PhD**

Department of Physiology, Faculty of Pharmacy, University of Belgrade, Serbia

Document Date: 12th January 2022

Clinical trial protocol

Test groups:

PsyCise trial is designed to quantify changes in clinical outcomes in participants treated for depression using personalized antidepressant dosing regimen, based on therapeutic drug monitoring (TDM) and CYP2C19 genotyping; as compared to the standard, “one size fits all” dosing. In order to reach this goal, we have defined two test groups based on the TDM findings. Namely, all participants who enter the trial (Visit 0) will begin taking standard escitalopram dose of 10 mg/day for two weeks when their blood samples will be taken for the purpose of TDM, and based on their steady state escitalopram concentrations they will be allocated to one of two groups at week 4 of the trial (visit 1):

- 1) “Standard dose” group: Participants will be allocated to this group if their TDM results at week 2 show their steady state escitalopram plasma concentrations were inside “therapeutic window” (25-50 ng/ml). For these participants, initial standard escitalopram dose of 10 mg/day is estimated to be optimal so they will continue to receive the same dose until the end of the trial at week 8 (visit 2).
- 2) “Adjusted dose” group: If TDM results at week 2 suggest that participant taking standard dose is underdosed or overdosed, given participant is allocated to this group. New, personalized dosing regimen will be produced for this participants based on steady state escitalopram plasma concentrations measured at week 2, and they will receive personalized escitalopram dose from week 4 (visit 1) until the end of the trial at week 8 (visit 2).

Course of the trial:

Week 0

Initial Visit (Visit 0 – V0)

- Participant will be enrolled at this point if inclusion criteria are met.
- Escitalopram monotherapy for Major Depressive Disorder in previously untreated patient will be initiated at standard dose of 10 mg/day.
- Outcomes measured:
 1. General and socio-demographic information
 2. Clinical questionnaires
 3. Anthropometric measurements
 4. Cardiological assessment
 5. Serum samples for biochemical analyses
 6. Buffy coat samples for DNA extraction and *CYP2C19* genotyping*

(*Sample is not time dependent, it can be taken at any visit)

Week 2

Mid-Visit (Vk)

- Escitalopram plasma concentrations reach steady state.
- Plasma sample taken for the purpose of TDM and group allocation.

- Percentages of participants who are underdosed and overdosed will be measured and used to confirm previous findings [Jukić 2018]

Week 4

Visit 1 (V1)

- Participants are allocated to the “Standard dose” or “Adjusted dose” group
- Independent clinician prescribes new dosing regimen to the participants in “Adjusted dose” group, and informs patients in “Standard dose” group to continue taking the same standard escitalopram dose.
- Clinician who usually monitors given patient is unaware of the group patient is allocated to, or the dose prescribed to a patient at Visit 1.
- Outcomes measured:
 1. Clinical questionnaires
 2. Anthropometric measurements
 3. Cardiological assessment
 4. Serum samples for biochemical analyses
 5. Plasma samples to reconfirm TDM findings in VK

Week 8

Visit 2 (V2)

- Final visit of the trial and the end of the follow-up.
- Outcomes measured:
 1. Clinical questionnaires
 2. Anthropometric measurements
 3. Cardiological assessment
 4. Serum samples for biochemical analyses
 5. Plasma samples to reconfirm TDM findings in VK and V1 for Standard dosing group, and to determine whether personalized dose is optimal for the patients in Personalized dosing group.

If needed, alternative course will be used:

Week 0

Initial visit + Mid-visit (V0+k)

- Participant on the stable (longer than 2 weeks) monotherapy of Major Depressive Disorder with standard dose of escitalopram (10 mg/day) will be enrolled if other inclusion criteria are met.
- Outcomes measured:
 1. General and socio-demographic information
 2. Clinical questionnaires
 3. Anthropometric measurements
 4. Cardiological assessment
 5. Serum samples for biochemical analyses
 6. Plasma sample for the purpose of TDM and group allocation.
 7. Buffy coat samples for DNA extraction and *CYP2C19* genotyping*

(*Sample is not time dependent, it can be taken at any visit)

Week 2

Visit 1 (V1) – *Identical to the standard protocol*

- Participants are allocated to the “Standard dosing” or “Personalized dosing” group
- Independent clinician prescribes new dosing regimen to the participants in “Personalized dosing” group, and informs patients in “Standard dosing” group to continue taking the same standard escitalopram dose.
- Clinician who usually monitors given patient is unaware of the group patient is allocated to, or the dose prescribed to a patient at Visit 1.
- Outcomes measured:
 1. Clinical questionnaires
 2. Anthropometric measurements
 3. Cardiological assessment
 4. Serum samples for biochemical analyses
 5. Plasma samples to reconfirm TDM findings in V_k

Week 6

Visit 2 (V2) – *Identical to the standard protocol*

- Final visit of the trial and the end of the follow-up.
- Outcomes measured:
 1. Clinical questionnaires
 2. Anthropometric measurements
 3. Cardiological assessment
 4. Serum samples for biochemical analyses
 5. Plasma samples to reconfirm TDM findings in V_k and V1 for Standard dosing group, and to determine whether personalized dose is optimal for the patients in Personalized dosing group.

Hypotheses:

- 1) More than one quarter of participants will be overdosed or underdosed under standard escitalopram dosing regimen (10 mg/day), as determined by TDM data 2 weeks after the beginning of the therapy.
- 2) Participants with escitalopram steady state plasma concentration outside the therapeutic window (“Adjusted dose” group) will experience reduced efficacy and more severe side effects of escitalopram therapy before dose personalization (at V1) compared to the participants with escitalopram levels within therapeutic window (“Standard dose” group) at standard dosing.
- 3) Participants with escitalopram steady state plasma concentration outside the therapeutic window (“Adjusted dose” group) will show improved efficacy and less severe side effects of escitalopram therapy after dose personalization (at V2) as compared to before (at V1), and will reach clinical outcomes comparable to the “Standard dose” group (at V2).

- 4) Decisions on whether to use personalized or standard dosing, and how to adjust personalized dose based on TDM data could have been determined before the beginning of the treatment using predictive model which, besides other predictors also includes *CYP2C19* genotyping data.

Statistical Analysis Plan

Primary outcomes:

To assess the efficacy of the escitalopram therapy under different dosing regimens we will use 21-item Hamilton rating scale for depression (HAM-D). Depression severity score will be measured at baseline (V0), at week 4 (V1) and week 8 (V2) after the beginning of the treatment. Since there is the need to compare depression severity scores between two test groups as well as between the visits V1 and V2, mixed analysis of covariance (Mixed ANCOVA) will be used if all assumptions associated with ANCOVA are met. Variables will be assigned as follows:

1. Dependent variable: Depression severity score measured by HAM-D scale
2. Independent variable - Fixed factor: Test group (Personalized vs Standard dosing)
3. Independent variable - Repeated measurements: Visit (Visit 1 vs Visit 2)
4. Covariates: Baseline HAM-D score (V0), Childhood trauma questionnaire score at V0, Age, Sex (Male=0, Female=1), Smoking status (0=Non-smoker, 1=Smoker), Alcohol consumption (0=No, 1=Yes), Metabolic syndrome diagnosed using siMS score [Soldatović 2016] (0=No, Yes)

Positive outcome: interaction between group and visit is significant ($\alpha=0.05$)

Besides using absolute HAM-D scores, we will also compare relative changes in HAM-D scores between V1 and V2 visits as another way to express the potential differences in therapy efficacy between the two test groups. If all needed assumptions are met, statistical test used will be analysis of covariance (ANCOVA) with variables assigned as follows:

1. Dependent variable: Relative change in HAM-D score between visits V1 and V2 calculated by formula:

$$\frac{HAMD_{V1} - HAMD_{V2}}{HAMD_{V1}}$$

2. Independent variable: Test group (Personalized dosing vs Standard dosing)
3. Covariables: Baseline HAM-D score (V0), Childhood trauma questionnaire score at V0, Age, Sex (Male=0, Female=1), Smoking status (0=Non-smoker, 1=Smoker), Alcohol consumption (0=No, 1=Yes), Metabolic syndrome (0=No, Yes)

Positive outcome: Test group is a significant factor ($\alpha=0.05$)

Other primary outcome we will use to quantify changes in clinical outcomes between test groups will be severity of the treatment side effects measured using clinician reported UKU (*Udvalg for Kliniske Undersogelser*) side effect rating scale. UKU scale rates 48 potential adverse reactions with intensity score ranging from 0 to 3 where score 3 signifies maximal intensity and score 0 signifies absence of the adverse reaction. Adverse drug reaction intensity scores for all 48 adverse reactions monitored with UKU scale will be measured at weeks 4 (V1) and 8 (V2) after the initiation of the escitalopram therapy. Due to large number of comparisons, significance measures will be adjusted using False Discovery Rate (FDR) correction. Absolute values of all 48 Adverse reaction scores will be compared between test groups and between two time points using mixed model analysis of covariance (Mixed ANCOVA) where variables will be assigned as follows:

1. Dependent variable: Adverse drug reaction score for the given adverse reaction measured by UKU scale
2. Independent variable - Fixed factor: Test group (Personalized vs Standard dosing)
3. Independent variable - Repeated measurements: Visit (Visit 1 vs Visit 2)
4. Covariables: Age, Sex (Male=0, Female=1), Smoking status (0=Non-smoker, 1=Smoker), Alcohol consumption (0=No, 1=Yes), Coffee consumption (0=No, 1=Yes), Use of psychoactive substances (0=No, 1=Yes), Metabolic syndrome (0=No, 1=Yes), Creatinine clearance, AST/ALT ratio.

Positive outcome: interaction between group and visit is significant ($\alpha=0.05$)

Alternatively, proportions of patients with intensity score greater than 0 (UKU scale intensity score >0 signifies the presence of the given adverse reaction) will be compared between the groups for all 48 adverse effect monitored with UKU scale at two time points: 4 weeks after the enrolment (V1) and 8 weeks after the enrolment (V2). Due to large number of comparisons, significance measures will be adjusted using False Discovery Rate (FDR) correction. Proportion of individuals in two test groups affected with the given adverse reaction will be compared using binary logistic regression analysis separately for visit V1 and visit V2 as follows:

1. Dependent variable: Frequency of the individuals affected with the given adverse drug reaction measured by UKU scale
2. Covariables: Test group (Personalized vs Standard dosing), Age, Sex (Male=0, Female=1), Smoking status (0=Non-smoker, 1=Smoker), Alcohol consumption (0=No, 1=Yes), Coffee consumption (0=No, 1=Yes), Use of psychoactive substances (0=No, 1=Yes), Metabolic syndrome (0=No, 1=Yes), Creatinine clearance, AST/ALT ratio.

Positive outcome: Test group is a significant factor ($\alpha=0.05$)

Secondary outcomes:

Retrospective TDM data on 2087 patients taking escitalopram [Jukić 2018] suggests that, in the clinical setting, about 40% of patients are expected to have their plasma escitalopram concentrations under the lower limit of the therapeutic window (25 ng/ml), and for about 10% of patients we expect to have plasma escitalopram levels above the upper limit of the therapeutic window (50 ng/ml). One of our aims is to try to confirm these findings using prospective study design which allows for the better control of the confounding factors compared to the retrospective data. Number of the patients with plasma escitalopram levels outside the therapeutic window under standard dosing regimen (10 mg/day) will be assessed using TDM data at Mid-Visit (VK), 2 weeks after the beginning of the therapy.

Big disadvantage of TDM guided establishment of the optimal drug exposure in the given patient is that it takes 4 weeks to personalize escitalopram dose and 2 more weeks to achieve optimal steady state drug concentrations. Alternative approach would be to build model that could predict optimal dose for every patient even before the initiation of the treatment. This model would have to include patient data on factors that could impact escitalopram exposure such as body weight, liver and kidney functions and genotype for the *CYP2C19* gene which is responsible for the interindividual variability in the rate of escitalopram metabolism in liver [Jukić 2018]. After all participants have finished the trial we will retrospectively build model using data collected during the trial, and then validate our model comparing it to the TDM method of dose personalization. For this purpose, all patients will be genotyped for *CYP2C19* gene and divided into 4 groups based on the enzymatic capacity of CYP2C19 enzyme:

1. Poor metabolizer (PM): Carries *2/*2, *2/*3 or *3/*3 *CYP2C19* genotype. Almost absent CYP2C19 enzyme activity
2. Intermediate metabolizer (IM): Carries *1/*2 or *1/*3 *CYP2C19* genotype. Reduced CYP2C19 enzyme activity
3. Normal metabolizer (NM): Carries *1/*1 *CYP2C19* genotype. Normal CYP2C19 enzyme activity
4. Ultra rapid metabolizer: Carries *1/*17 or *17/*17 *CYP2C19* genotype. Increased CYP2C19 enzyme activity

Multiple linear regression model will be build using selected variables:

1. Dependent variable: Plasma escitalopram concentrations at Week 2 (Vk) after the initiation of the treatment
2. Independent variables: Body mass index, PM status (0=Yes, 1=No), IM status (0=Yes, 1=No), NM status (0=Yes, 1=No), UM status (0=Yes, 1=No), Creatinine clearance, AST/ALT ratio

Other outcome measures/observations:

To further validate our primary outcome measures: escitalopram treatment efficacy and severity of adverse effects, we will use Clinical Global Impression (CGI) scales. Scores will be determined for all 3 CGI scales: for Severity of illness (CGI-S) scale at baseline, visit 1 and visit 2, and for Global improvement (CGI-I) scale and for Efficacy Index (CGI-E) at visits 1 and 2. Differences in all 3 CGI scales between visits 1 and 2 will be compared between test groups separately using ANCOVA tests with the equivalent sets of covariates to the ones used for HAM-D scale.

In all patients at baseline and at visits 1 and 2, electrocardiography will be performed in order to monitor potential QT interval prolongation. We will test for correlation between QT interval length and escitalopram plasma levels at various visits, and also we will compare changes in QT interval length between visit 1 and visit 2 in both test groups using mixed ANCOVA test adjusting for the baseline QT length.

Due to high comorbidity of anxiety and depression, and since escitalopram is frequently prescribed in anxiety disorders, we will explore severity of anxiety symptoms in all participants at baseline (V0), Week 4 (V1) and Week 8 (V2) of the treatment by using clinician reported Hamilton anxiety rating scale (HAM-A). Severity of anxiety symptoms will be compared between two test groups at two time points (V1 and V2) using mixed analysis of covariance (Mixed ANCOVA). Variables to be considered as covariates will be: Baseline HAM-A score (V0), Childhood trauma questionnaire score at V0, Age, Sex (Male=0, Female=1), Smoking status (0=Non-smoker, 1=Smoker), Alcohol consumption (0=No, 1=Yes), Metabolic syndrome (0=No, Yes).

Alongside with HAM-A scale we will also use serum cortisol levels as a biomarker for anxiety disorders in our population. Cortisol levels will be analyzed in a similar way to HAM-D and HAM-A scores using mixed analysis of covariance (Mixed ANCOVA) with covariates being: Baseline Cortisol serum levels (V0), Childhood trauma questionnaire score at V0, Age, Sex (Male=0, Female=1), Smoking status (0=Non-smoker, 1=Smoker), Alcohol consumption (0=No, 1=Yes), Metabolic syndrome (0=No, Yes). Additionally, correlation between HAM-A score and cortisol levels will be tested.

Since stress, trauma and socio-economic status can all be a part of depressive disorder pathogenesis, we will explore these environmental factors in order to determine their role in the clinical pictures of our participants. Outcome measures used will be:

1. Perceived stress score measured at baseline, visit 1 and visit 2,
2. Childhood trauma score measured at baseline,
3. Employment status (1=Unemployed, 2=Employed; monthly incomes <40 000 RSD, 3=Employed; monthly incomes 40 000-80 000 RSD, 4=Employed; monthly incomes >80 000RSD).
4. Marital status (1=Unmarried, 2=Married, 3=Divorced, 4=Widowed)
5. Education level (1=Primary education (8 years), 2= High school diploma (8+3 or 8+4 years), 3= Associate's degree (8+4+2 or 8+4+3 years) 4= Bachelor's degree (8+4+4 years or higher)

We will separately test for the correlation between these variables and HAM-D score, HAM-A score and CGI-S score.

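### No prespecified analysis isolates what CYP2C19 genotyping adds, and no HAM-D or UKU result can show benefit from genotype-guided dosing

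*Combined protocol and SAP*

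**What the plan says.** The protocol's title names both plasma level monitoring and CYP2C19 genotyping. The aim under Test groups describes a "personalized antidepressant dosing regimen, based on therapeutic drug monitoring (TDM) and CYP2C19 genotyping", set against standard dosing.

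The next sentence of the same section says "we have defined two test groups based on the TDM findings". For the Adjusted dose group, "New, personalized dosing regimen will be produced for this participants based on steady state escitalopram plasma concentrations measured at week 2". The note on the genotyping sample, under Course of the trial, reads "Sample is not time dependent, it can be taken at any visit".

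Hypothesis 4 concerns genotype. It proposes that the choice between standard and personalized dosing, and the size of the adjustment, "could have been determined before the beginning of the treatment using predictive model which, besides other predictors also includes" CYP2C19 genotyping data. The Statistical Analysis Plan, Secondary outcomes, adds: "After all participants have finished the trial we will retrospectively build model using data collected during the trial". The model is then to be validated against the TDM method. It is a multiple linear regression of week 2 plasma concentration. Its predictor list begins "Independent variables: Body mass index, PM status (0=Yes, 1=No), IM status (0=Yes, 1=No" and continues with NM status, UM status, creatinine clearance and AST/ALT ratio.

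**The concern.** Half of the title question is about genotyping, and the plan has no analysis set up to answer that half.

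On the clinical side, nobody's dose depends on genotype. If the aim sentence stands, a reader of the HAM-D and UKU results could take them as outcomes of a regimen that combined TDM with genotype.

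On the prediction side, the model mixes genotype with three variables that need no genetic test. If the only result is how well the whole model matches TDM, the reader cannot tell whether the match comes from genotype, from the other variables, or from both. The plan states no performance measure and no success criterion for this model, whereas the HAM-D and UKU analyses each have one.

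**Working it through.** The documents give no sample size, effect size or accuracy target for this model, so there is no planned figure to reproduce. The check has four parts.

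**1. Where genotype is used**

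| Step | Basis stated in the plan | Genotype used? |
|---|---|---|
| Allocation to group (Test groups) | Week 2 plasma concentration against 25-50 ng/ml | No |
| Adjusted dose (Test groups) | "based on steady state escitalopram plasma concentrations measured at week 2" | No |
| HAM-D, UKU, CGI, QT, HAM-A and cortisol analyses (SAP) | Test group or visit, plus listed covariates | No |
| Regression of week 2 concentration (SAP, Secondary outcomes) | BMI, four phenotype indicators, creatinine clearance, AST/ALT ratio | Yes |

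The genotype sample may be drawn at any visit, including after the dose decision at Visit 1, and the model is built after the last participant finishes. Under this plan genotype cannot inform a trial dose.

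**2. Whether the listed regression can be fitted**

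The plan places every patient in one of four phenotype groups and codes each indicator 0=Yes, 1=No. Each patient therefore has one 0 and three 1s, and the four indicators always sum to 3. That is a constant multiple of the intercept column. The design has 1 + 3 + 4 = 8 columns; a numerical check gave rank 7. Separate genotype coefficients cannot be estimated until one indicator is dropped.

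**3. What the corrected regression could show**

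With one phenotype as reference, three genotype terms remain. Their joint test in the full model is the same test as comparing the models with and without genotype:

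F = [(R²_full − R²_base)/3] / [(1 − R²_full)/(n − 7)]

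In one simulated data set (n = 100, assumed phenotype shares and effects), R² was 0.1314 without genotype and 0.3299 with it. So F = (0.1985/3)/(0.6701/93) = 9.19, p = 2.2e-05. The joint Wald test of the three terms gave the same F and p. The information on genotype is in the data; the plan does not say that it will be extracted.

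**4. What agreement with TDM alone would show**

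Inputs: about 40% of patients below 25 ng/ml and about 10% above 50 ng/ml (SAP, Secondary outcomes). Assumption: concentrations are log-normal.

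- Log-SD = ln(50/25)/(1.2816 + 0.2533) = 0.6931/1.5349 = 0.452
- Median = exp(ln 25 + 0.2533 × 0.452) = 28.0 ng/ml

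Classify each patient as below, in or above the window from a point prediction, and compare with the measured class:

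| Assumed R² (log scale) | Agreement with TDM |
|---|---|
| No model, everyone called in-window | 50% |
| 0.1 | 53.9% |
| 0.2 | 57.4% |
| 0.3 | 60.7% |
| 0.4 | 63.8% |

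Each 0.1 of R² moves agreement by 3 to 4 points. A result near 64% would fit a model in which genotype supplies nearly all of the R², and equally one in which the other variables reach 0.3 (61%) and genotype adds the last 3 points. The split is an illustration. The documents give no R², name no three-class measure and list the concentration without a log transform.

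**The case against.** A reader might infer that no result of this trial can show that genotyping adds anything. The documents do not support that. The planned analysis is a multiple regression, so once a reference phenotype is chosen its genotype terms are already adjusted for BMI, creatinine clearance and AST/ALT ratio, and their joint test is the nested comparison. The missing comparison could also be run later on the same data. This objection stands. What remains is that the plan neither names the test nor lists the indicators in a form from which separate genotype effects can be estimated.

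It can also be said that the aim is one loose sentence, put right by the text around it. The next sentence ties the groups to TDM, hypotheses 2 and 3 speak only of plasma concentration, and hypothesis 4 openly presents genotype as one predictor among several in a retrospective model. That is fair, and nothing in the documents says that the model's accuracy would be credited to genotype alone or that the clinical results would be presented as genotype-based. Even so, the aim sentence conflicts with the dosing rule as written, and a sentence that states the aim should not need correcting by its context.

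Finally, the model is secondary and touches no allocation, dose or primary test. That limits the weight of the point without removing it.

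**Conclusion.** The point holds in a limited form. The reading of the text needs no assumption: genotype enters no allocation, dose or clinical outcome analysis, and the one model containing it is validated only as a whole. It follows that no HAM-D or UKU comparison can show benefit from genotype-guided dosing, and that the planned validation against TDM cannot separate genotype from the other predictors. Added prediction of concentration can be shown, but only by an analysis the plan does not specify. Added prediction would still not be clinical utility, because no participant is dosed by genotype.

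The collinearity follows from the coding in the plan. The agreement figures of 50% to 64% rest on the log-normal assumption and the assumed R² values; they show how little a combined figure reveals, not how large genotype's share is. This should be changed, although it does not threaten the primary tests.

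**What to change.** 1. **Hypothesis 4 and the SAP, Secondary outcomes.** Choose one phenotype as reference. On the same patients, fit (a) BMI, creatinine clearance and AST/ALT ratio, and (b) these plus the three CYP2C19 terms. Report the joint test of the three terms, the change in R², and the change in below/in/above-window agreement with TDM, with 95% confidence intervals. Use internal validation, because the model is fitted to the same week 2 concentrations that define the TDM comparator. Base any statement about genotyping on this increment, and call it added prediction of exposure, not clinical utility.

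2. **Aim under Test groups.** Reword it so that the HAM-D and UKU comparisons are outcomes of TDM-based adjustment, with genotyping evaluated only in the retrospective predictive model.

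The cost is one extra regression on data already collected and some changes of wording; no visit, sample or dose changes. The downside is that the genotyping claim may become smaller. Precision should also be considered. With an assumed base R² of 0.10, alpha 0.05 and 80% power, the 3-degree-of-freedom test (noncentrality N × ΔR²/(1 − 0.10 − ΔR²)) needs about 190 patients for an R² gain of 0.05, 92 for 0.10 and 43 for 0.20. The documents state no sample size to set against these.

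### The primary tests compare non-randomized concentration strata but are labelled and judged as personalized versus standard dosing; the UKU logistic success rule is wrong as written

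*Combined protocol and SAP*

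**What the plan says.** **Aim and allocation (Test groups; Course of the trial).** The aim reads: "PsyCise trial is designed to quantify changes in clinical outcomes in participants treated for depression using personalized antidepressant dosing regimen", set against a uniform standard dose. Everyone starts on 10 mg/day, and "based on their steady state escitalopram concentrations they will be allocated to one of two groups at week 4 of the trial (visit 1". Participants within 25-50 ng/ml stay on 10 mg/day; those outside get a new regimen from V1. No randomization is described. The alternative course admits a "Participant on the stable (longer than 2 weeks) monotherapy" at that dose, and the enrolment visit supplies the "Plasma sample for the purpose of TDM and group allocation".

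**Hypotheses.** Hypothesis 2 predicts that out-of-window participants "will experience reduced efficacy and more severe side effects of escitalopram therapy before dose personalization (at V1" than those in window. Hypothesis 3 predicts that they improve from V1 to V2 "and will reach clinical outcomes comparable to the" Standard dose group at V2.

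**Primary outcomes (SAP).** For HAM-D, "Depression severity score will be measured at baseline (V0), at week 4 (V1) and week 8 (V2". There are four primary analyses, each with a success line at 0.05:
- HAM-D mixed ANCOVA at V1 and V2, with "Independent variable - Fixed factor: Test group (Personalized vs Standard dosing". Success is a significant group-by-visit interaction.
- HAM-D relative change, a per-patient (V1 - V2)/V1 in an ANCOVA. Success is a significant group term.
- UKU mixed ANCOVA, one per item for 48 items, FDR-adjusted. Success is a significant interaction.
- UKU logistic regression, offered as an alternative, per item and separately at V1 and V2, FDR-adjusted. One success line covers both visits: a significant group term.

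The only assumptions mentioned are the usual ones for ANCOVA.

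**The concern.** Hypotheses 2 and 3 describe the strata accurately. The aim, the factor label and the success lines go further, because they treat a significant term as evidence about dosing regimens. No out-of-window participant stays on the starting dose, so the data contain no direct comparison of adjusting with not adjusting. The pattern that hypotheses 2 and 3 predict, a gap at V1 that closes by V2, is also what slower responders catching up on an unchanged dose would show. What is at stake is the conclusion that the primary analyses may support.

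**Working it through.** The plan gives no figure to reproduce: there is no sample size, SD, power or expected difference. The check is structural, with small illustrations.

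**1. What the interaction estimates.** Let D be the effect of the dose change on V1-to-V2 improvement in the Adjusted group. Let δ be the difference in improvement (Adjusted minus Standard) that would have occurred with no dose change. The interaction estimates D + δ, and the design identifies only the sum.
- Catch-up: D = 0, δ = +2 points gives 2. No dosing effect, but an apparent benefit.
- Persistently slower improvement out of window: D = 2, δ = -2 gives 0. A real benefit is hidden.

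**2. Assumption needed for a dosing reading, by test** (strata compared as if no dose had been changed):
- HAM-D and UKU interactions: equal mean absolute V1-to-V2 change.
- Relative-change ANCOVA: equal mean relative change.
- V2 logistic regression: equal risk at V2.
- V1 logistic regression: none will do. Everyone is still on 10 mg/day, so the effect of adjustment is zero by design.

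**3. Do the two HAM-D assumptions agree?** When V1 means differ and scores are changing, they are different conditions and generally do not coincide. With uniform change within strata and assumed V1 means of 16 and 14, a 4-point fall is 4/16 = 25% against 4/14 = 29%. Conversely, an equal 30% fall gives absolute changes that differ by 0.3 × 2 = 0.6 points. They can coincide, because the SAP averages per-patient ratios. Suppose every Adjusted patient goes 20→15, and Standard patients go half 12→10 and half 24→16. V1 means are 20 and 18. Mean absolute change is 5 and (2 + 8)/2 = 5. Mean relative change is 25% and (16.7% + 33.3%)/2 = 25%.

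**4. Do the covariates help?** The mixed ANCOVAs list covariates but no covariate-by-visit terms. A covariate that is constant over time and enters as a main effect cancels from the V1-to-V2 difference. One simulated data set shows this (100 per group, no dose effect, mean age 40 and 46, V2 score rising 0.2 points per year of age). The interaction was 1.587 with no covariate, 1.587 with age as a main effect, and 0.193 with age-by-visit added. The planned adjustment reaches the interaction only if such terms are fitted.

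**5. UKU logistic success line.** There are 48 items × 2 visits = 96 tests under one line. The 48 tests at V1 can bear only on hypothesis 2. At V2, if comparable means equal risk, the line is met at about the nominal 5% per item before FDR; a persisting disadvantage of the Adjusted group would meet it more often.

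**6. Direction.** None of the success lines states one. An interaction in which the Adjusted group improved less would also count.

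**7. Illustrative power for an assumed δ (HAM-D interaction, D = 0).** Equal groups follow the SAP's expected 40% + 10% = 50% outside the window. SE = SD × √(1/n1 + 1/n2), two-sided 5%, unadjusted; SDs of 5, 6 and 8 for change and the group sizes are assumed.
- δ = 2, 100 per group: 81% / 65% / 42%.
- δ = 2, 50 per group: 52% / 39% / 24%.
- δ = 0.5: 7% to 11% with 100 per group, 6% to 8% with 50.

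These show only how readily a difference of that size would be detected.

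**The case against.** The strongest reply is that the design is disclosed. The protocol says openly that groups follow the TDM result, and hypotheses 2 and 3 are written about strata. Personalized and Standard dosing also serve as plain group names in the visit schedule. The success lines are significance rules, and the SAP draws no causal conclusion from them. V1 is a measurement before the dose change, the usual clinician is blinded to group and dose, and covariates are planned. A non-randomized design is a legitimate choice.

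Much of this stands, and it is why most of the point concerns wording and interpretation. It does not supply the missing assumption. Blinding limits rating bias, not differing trends. The HAM-D covariates also omit body weight, liver and kidney function and genotype, which the SAP itself names under Secondary outcomes as possible influences on exposure.

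A reader might infer four stronger things that the documents do not support:
- That the two HAM-D assumptions can never both hold. The example in step 3 shows that they can.
- That the bias always favours personalization. Hypothesis 2 predicts a poorer response out of window by V1; if that persisted on an unchanged dose, the interaction would understate a benefit.
- That the percentages in step 7 are the trial's false-positive rates. They are power for assumed shifts.
- That the logistic line is certain to be met at V1, or can be met only by chance at V2. Hypothesis 2 concerns side-effect severity overall, not the prevalence of each item; power and FDR intervene; and comparable is not defined as identical.

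**Conclusion.** The point holds, and its core rests on the documents alone. Allocation is wholly determined by concentration, every out-of-window participant is adjusted, and nobody is adjusted before V1. All the primary tests are therefore non-randomized comparisons of strata. A significant term shows a dosing effect only under an assumption that the plan does not state and that differs by test. Neither the size nor the direction of any bias can be derived from the documents.

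The aim, the factor label, the interaction lines and the relative-change line should be fixed. The UKU logistic success line must be: it is wrong as written at both visits, counting at V1 a difference that dosing cannot have caused and at V2 one that runs against hypothesis 3.

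**What to change.** (a) Rename the factor in all primary analyses: concentration status at the allocation sample (out of window, dose adjusted at V1, versus in window, dose unchanged).

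(b) Restate the aim and the success lines for the interactions and relative change as non-randomized differences between strata in V1-to-V2 change. State the direction that supports hypothesis 3, namely greater improvement in the Adjusted group.

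(c) Label the V1 logistic regression a pre-adjustment comparison for hypothesis 2. At V2, replace the success line with the group odds ratio and its confidence interval, read against hypothesis 3's prediction of comparable outcomes.

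(d) Beside each test, state the assumption from step 2, conditional on the covariates. Include covariate-by-visit terms in the mixed ANCOVAs so that the condition is true of the model. Name before analysis which HAM-D scale, absolute or relative, a dosing interpretation would rest on.

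(e) As indirect evidence only, report V0-to-V1 HAM-D change by stratum in the standard course, with its direction. Note that hypothesis 2 already predicts a smaller improvement out of window and that, if this persisted on an unchanged dose, the interaction would understate a benefit. Equal change before V1 would not prove equal change after it. The check is not available for UKU, for which the SAP plans no V0 score, and does not carry over to the alternative course, where V0 is already on treatment.

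**Cost.** Wording, one table from HAM-D scores already planned, and one extra term per covariate (7 in the HAM-D mixed ANCOVA, 9 in each UKU one). No new visits, samples or participants. The downside is a weaker headline claim.
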